10.3.2 Contraception Guidance

- Participants of childbearing potential are eligible to participate if they agree to use a highly effective method of contraception consistently and correctly as described in Table 9 from Screening (signing the ICF) until at least 6 months after IP administration.
- Male participants with a pregnant or breastfeeding partner must agree to remain abstinent
 from penile-vaginal intercourse or use a male condom during each episode of penile
 penetration. In addition, male participants must refrain from donating sperm from
 Screening (signing the ICF) until at least 6 months after the last dose of IP administration.
 Participants with a partner or partners who is (are) not of childbearing potential are exempt
 of these requirements.

Table 9 Highly Effective Contraceptive Methods

Highly Effective Contraceptive Methods that are User Dependent^a

Failure rate of <1% per year when used consistently and correctly.

Combined (estrogen and progestogen containing) hormonal contraception associated with inhibition of ovulation^b

- Oral.
- Intravaginal.
- Transdermal.

Progestogen-only hormonal contraception associated with inhibition of ovulation

- Oral.
- Injectable.

Highly Effective Contraceptive Methods that are User Independent^a

- Implantable progestogen-only hormonal contraception associated with inhibition of ovulation^b
- Intrauterine device (IUD).
- Intrauterine hormone-releasing system (IUS).
- Bilateral tubal occlusion.
- Subdermal progestogen implant.

Vasectomized partner

A vasectomized partner is a highly effective birth control method provided that the partner is the sole sexual partner of the WOCBP and the absence of sperm has been confirmed. If not, an additional highly effective method of contraception should be used.

Sexual abstinence

Sexual abstinence is considered a highly effective method only if defined as refraining from heterosexual intercourse during the entire period of risk associated with the IP. The reliability of sexual abstinence needs to be evaluated in relation to the duration of the study and the preferred and usual lifestyle of the participant.

NOTES:

a. Typical use failure rates may differ from those when used consistently and correctly. Use should be consistent with local regulations regarding the use of contraceptive methods for participants participating in clinical studies.
b. Hormonal contraception may be susceptible to interaction with the IP, which may reduce the efficacy of the contraceptive method. In this case, 1 highly effective method of contraception and a barrier method (condom) should be utilized starting at Screening and throughout the study period up to 6 months after IP administration.
NOTE: Condoms alone are not highly effective methods of contraception. Periodic abstinence, the rhythm method, and the withdrawal method are not acceptable methods of birth control.

Pregnancy Testing

- WOCBPs should only be included in the study after a confirmed menstrual period and a
 negative highly sensitive serum pregnancy test. For WOCBPs using hormonal
 contraceptives which may result in menstrual suppression, a negative serum pregnancy
 test is sufficient for enrollment.
- All subsequent pregnancy testing will be performed using a highly sensitive urine pregnancy test that will be performed at time points specified in the Schedule of Assessments (Table 1) and as required locally. Any positive urine pregnancy test result will be confirmed with a serum β-human chorionic gonadotropin (β-hCG) test.

• Pregnancy testing will be performed whenever a menstrual cycle is missed or when pregnancy is otherwise suspected.

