8.7.4 Follow-up of AEs and SAEs

After the initial AE/SAE report, the PI or designee is required to proactively follow each participant at subsequent visits/contacts. All AEs/SAEs and AESIs (as defined in Section 8.7.7) documented at a previous visit/contact that are designated as ongoing will be followed up until resolution, stabilization, the event is otherwise explained, or until the participant is lost to follow-up (as defined in Section 7.3). This activity will continue up to Day 75 (11 weeks after IP administration). The PI or designee will ensure that follow-up includes any supplemental investigations as medically indicated or requested by the Medical Monitor and/or Sponsor to elucidate the nature and/or causality of the AE or SAE as fully as possible. This may include additional laboratory tests or investigations, histopathological examinations, or consultation with other health care professionals. For AEs or SAEs that are reported before or on Day 75, follow-up of ongoing events that are considered related to the IP will continue only up to the time of database lock.

The PI or designee is not obligated to actively seek new AEs or SAEs after conclusion of the study participation. However, if the PI or designee learns of any SAE, including a death, at any time after a participant has been discharged from the study, and he/she considers the event

to be reasonably related to the IP or study participation, the PI or designee must promptly notify the Sponsor.

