8.7.6 Pregnancy

There is no information about the effects that AVT05 could have on the development of the fetus in humans. Therefore, it is important that WOCBPs and participants' partners do not become pregnant until at least 6 months after IP administration and agree to use adequate contraception during this period.

Details of all pregnancies in WOCBPs and participants' partners (after obtaining the necessary signed informed consent from the pregnant partner directly) will be collected via a Pregnancy Report Form from the time of IP administration until at least 11 weeks after IP administration. Since this is a single dose study, participants who become pregnant during the study will be encouraged to remain in the study and will be followed for safety up to EoS visit. Only those follow-up procedures that would not expose the participant to additional undue risk will be performed.

The PI or designee will record pregnancy information on a Pregnancy Report Form and submit it to the Sponsor and/or designee within 24 hours of the site's awareness of the pregnancy. The procedures for completing and transmitting pregnancy reports and contact information for pregnancy reporting can be found in the Pregnancy Report Form.

The pregnant participant or partner will also be followed up to determine the outcome of the pregnancy, including spontaneous or voluntary termination. The PI or designee will collect follow-up information on the pregnant participant or partner and the child (including details of

the birth, and the presence or absence of any birth defects, congenital abnormalities, or maternal and/or newborn complications) and the information will be forwarded to the Sponsor. Generally, the follow-up period for a pregnancy will be deemed to have ended when the health status of the child has been determined on its birth. Any termination of the pregnancy will be reported regardless of fetal status (presence or absence of anomalies) or indication for the procedure.

While pregnancy itself is not considered to be an AE or SAE, hospitalizations for complications during pregnancy, or if the outcome of the pregnancy meets the criteria of an SAE (eg, spontaneous abortions, fetal death, stillbirth, congenital anomalies [including those in an aborted fetus], ectopic pregnancy) or elective termination of a pregnancy will be reported as an SAE (Sections 8.7.3 and 8.7.5).

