Nervous system (including psychiatry)	Common: Dizziness, headache, paresthesia, Depression, insomnia Uncommon: Balance disorders Rare: Demyelinating disorders (central and peripheral), dysgeusia	1) 2)	Standard monitoring as with all early phase trials Participants with a history of demyelinating conditions will be excluded (see Section 5.2)

Target System	Effect	Risk Mitigation
Gastrointestinal system	Common: Dyspepsia, gastrointestinal and abdominal pain, nausea, gastrointestinal inflammatory disorders (such as gastritis and colitis), stomatitis Uncommon: Constipation, gastroesophageal reflux disease	 Standard monitoring as with all early phase trials Any self-reported GI disturbance will be investigated further with appropriate investigation
Skin & Connective Tissue	Common: Pruritus, rash, alopecia, dermatitis Uncommon: Bullous skin reactions, psoriasis (new onset or worsening of preexisting psoriasis, palmar/plantar and pustular), urticaria Rare: Lichenoid reactions, skin exfoliation, vasculitis (cutaneous), Lupus-like syndrome Not known: Worsening of symptoms of dermatomyositis	Standard monitoring and regular AE checks as with all early phase trials
Reproductive system	Uncommon: Breast disorders, menstrual disorders	 Specific contraceptive requirements will be in place for participants Contraceptive guidance will be used in inclusion criteria WOCBP will need evidence of negative pregnancy tests prior to dosing
Endocrine disorders	Uncommon: Thyroid disorder (such as hypothyroidism, hyperthyroidism and goiter), Blood glucose increased, lipids increased	 Standard monitoring as with all early phase trials Participants with known diabetes will be excluded from the study
Ophthalmology	Uncommon: Visual disorders (such as blurred vision and decreased visual acuity), conjunctivitis, eye allergy (such as pruritis and irritation)	 Standard monitoring as with all early phase trials Any self-reported visual disturbance will be investigated further with thorough examination
General disorders and administration site conditions	Common: Pyrexia, asthenia, injection site reaction (such as injection site erythema, urticaria, induration, pain, bruising, pruritus, irritation and paresthesia), chest discomfort Rare: Impaired healing	 Standard monitoring as with all early phase trials Regular injection site checks
Injury, poisoning and procedural complications	Common: Bone fractures	Standard monitoring as with all early phase trials

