Section 4.5.1 Study Stopping Criteria	 Stopping criteria were revised from >2 to ≥1 participants with an SAE that is at least possibly related to the IP. A new stopping criterion was added to stop dose escalation if there are ≥2 participants in the same group with severe non-serious AEs which are at least possibly related to the IP. 	As recommended by MEDSAFE based on EMA guidelines on study stopping criteria.
Section 5.1 Inclusion Criteria, Criterion no. 6	Text was revised to clarify that vital signs limits for inclusion apply "during screening and Day 1 prior to dosing of IP."	To add clarity.
Section 5.1 Inclusion Criteria, Criteria no. 11	The requirement to discuss with Sponsor, for repeating evaluations for laboratory tests was changed to permit repeats at the discretion of PI or delegate.	For operational reasons, based on feedback from site.
Section 5.1 Inclusion Criteria, Criteria no. 12	Included text "negative for" to clarify that negative test reports are required for viral serology and β-D glucan tests for inclusion in the study.	Editorial – typographical error corrected.
Section 5.1 Inclusion Criteria, Criteria no. 14	New criterion added to specify restriction for donating ova/eggs for female participants.	Added as an additional safety measure.
Section 5.3.2 Caffeine, Alcohol, and Tobacco	Changed restriction on smoking from ≤10 cigarettes or equivalent per day to ≤10 cigarettes or equivalent per week.	Editorial – error corrected.
Section 10.1 Regulatory, Ethical, and Study Oversight Considerations, Informed Consent Process	The word "pharmacogenomic" removed from the text regarding consent for optional exploratory research.	Editorial change. There will be no pharmacogenomic testing as part of optional exploratory research.
Section 10.2 Clinical Laboratory Tests, Table 9	 Removed pathogens from list of urinalysis dipstick tests. Added coagulation panel. 	Tests not done at site.Error of omission.
Throughout the protocol	Minor editorial changes were made.	Minor, and therefore have not been summarized

Version 3.0 (10 November 2022)

Overall Rationale for the Amendment:

[figure not shown]
The protocol was amended primarily to remove some typographical and editorial errors and provide some clarity on some aspects of the study. A summary of the changes with rationale for each change is provided below.

Description of Changes in Amendment

Section # and Name	Description of Change	Brief Rationale

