Section 5.1 Inclusion Criteria, Criterion no. 12, Section 1.3 Schedule of activities, Table 8	 Changed from "HBsAb" to "Anti-HBS". Included note to specify participants with positive anti-HBs alone will be eligible if they have documented history of vaccination 	To prevent exclusion of participants who test positive for anti-HBs due to vaccination.
Section 5.1 Inclusion Criteria, Criteria no. 13, 14, 15, and 16, Section 8.7.6, Section 10.3 Contraceptive and barrier guidance	Revised the duration for contraception and other precautions for pregnancy after the end of study, from 11 weeks to at least 6 months	To align with the contraceptive timeframe specified in the Simponi SmPC.
Section 6.3.2 Blinding	Added text "using blinded/unblinded teams"	To add clarity for the site blinding procedures.
Section 8.7.3 Reporting of serious adverse events	Added text for the PI to report clinically or medically significant updated SAEs to the Sponsor/designee within 24 hours of having such information.	As per local regulatory guidelines.
Throughout the protocol	Minor editorial changes were made.	Minor, and therefore have not been summarized

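### As worded, the exemption in Section 10.3.2 lifts the sperm-donation ban for men whose partners are not of childbearing potential; the ban should apply to all male participants

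*Combined protocol and SAP*

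**What the plan says.** The second bullet of Section 10.3.2 (Contraception Guidance) has three parts, in this order:

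1. Condom or abstinence: "Male participants with a pregnant or breastfeeding partner must agree to remain abstinent" or else use a condom.
2. Donation: "In addition, male participants must refrain from donating sperm from" Screening until at least 6 months after dosing. No partner condition is attached.
3. Exemption: "Participants with a partner or partners who is (are) not of childbearing potential are exempt" from the requirements just stated. The reference is plural, and nothing restricts it to part 1.

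Other sections bear on the same rule:

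- Section 8.7.6 gives the reason for the precautions: "There is no information about the effects that AVT05 could have on the development of the fetus in humans". It asks that female participants of childbearing potential, and participants' partners, not become pregnant for at least 6 months after dosing.
- Section 10.4, in the reproductive-system row, says "Contraceptive guidance will be used in inclusion criteria", so Sections 5.1 and 10.3 are meant to agree.
- Section 10.5, under Version 2.0, records for criterion 14 of Section 5.1: "New criterion added to specify restriction for donating ova/eggs for female participants". Under Version 3.0 it records that the precautions were lengthened from 11 weeks to at least 6 months, at "Section 5.1 Inclusion Criteria, Criteria no. 13, 14, 15, and 16, Section 8.7.6, Section 10.3 Contraceptive and barrier guidance".

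**The concern.** A sperm-donation ban protects a recipient who is not the participant's partner. Whether his own partner is postmenopausal or sterilised does not change that recipient's situation, so an exemption keyed to the partner has no rationale here. The plan offers none.

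A site applying the bullet literally could tell a man with such a partner that he may donate within 6 months of dosing. If Section 5.1 bans donation outright, sites instead hold two conflicting instructions. Pregnancy reporting would not be expected to reveal the problem, because Section 8.7.6 collects pregnancies in participants and their partners, and a recipient of donated sperm is neither.

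What is at stake is a participant-protection instruction. The primary analysis is not touched.

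**Working it through.** No arithmetic applies; the check is a reading of the text. The inputs are the three sentences of the male bullet and the definition of childbearing potential in Section 10.3.1. That definition is written for participants and is applied here to partners.

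**What each type of male participant is told**

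| Man's situation | Condom/abstinence duty | Donation ban before exemption | Exemption applies? | Donation ban after exemption |
|---|---|---|---|---|
| Partner pregnant or breastfeeding | Yes | Yes | Almost never (see below) | Stays |
| Partner of childbearing potential, neither pregnant nor breastfeeding | None stated | Yes | No | Stays |
| Partner not of childbearing potential | None stated, unless she is breastfeeding | Yes | Yes | Lifted |
| No partner | None stated | Yes | No | Stays |

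**Can the exemption be confined to the condom duty?** That duty reaches only men with a pregnant or breastfeeding partner. Section 10.3.1 removes childbearing potential only for premenarchal, sterilised (hysterectomy, bilateral salpingectomy or bilateral oophorectomy) and postmenopausal women. A pregnant partner will ordinarily be in none of these groups. A breastfeeding partner will usually be in none either, unless she has been sterilised. The narrow reading therefore leaves the exemption almost empty. In the table, the only row in which it makes a practical difference is the third, and there the duty it removes is the donation ban.

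**Is the result coherent?** The third and fourth rows differ only in whether the man has a partner who cannot conceive. One may donate and the other may not, although a recipient's position is the same in both.

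**Does another available section restore the ban?** None does. Section 8.7.6 speaks of participants and their partners, not recipients of donated sperm. The amendment history shows an egg-donation restriction in Section 5.1, but not whether a matching sperm criterion exists. Section 5.1 has to be checked directly, with two cases:

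- If it bans donation for all men, Section 10.3.2 contradicts it.
- If it repeats the exemption or is silent, Section 10.3.2 releases the men in the third row.

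Section 10.3.2 needs correcting in either case.

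**The case against.** The strongest case against is that eligibility is set in Section 5.1, which this review could not see. A general sperm-donation criterion among numbers 13 to 16 is plausible, given the egg-donation criterion and the stated link between those criteria and the contraceptive guidance. The authors also probably meant to exempt only the condom duty, so this may be a drafting slip. Both points stand. They limit the consequence and the weight of the finding, but they do not make the sentence in Section 10.3.2 correct.

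A second objection also stands: simply attaching the exemption to the present condom sentence would leave it nearly empty. The bullet states no contraceptive duty for men whose partners can conceive but are not pregnant or breastfeeding, although Section 8.7.6 wants partners not to become pregnant. The repair has to deal with this too.

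A reader might infer more than the documents support:

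- **That the sponsor chose to let these men donate, or that the protocol as a whole has no general ban.** Neither can be said without Section 5.1.
- **That sperm exposure to AVT05 is a known hazard.** The available text says only that fetal effects are unknown. It describes no transfer through semen and no effect on sperm, so it supports a precaution and no more.
- **That the gap between the 6-month ban and the end of AE follow-up measures the problem.** Section 8.7.4 says of follow-up: "This activity will continue up to Day 75 (11 weeks after IP administration". That gap is the same for every male participant and would remain if the bullet were perfectly worded.

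**Conclusion.** The point holds as a minor participant-protection correction. As written, Section 10.3.2 lifts the sperm-donation ban for men whose partners are not of childbearing potential, and the plan gives no reason for doing so.

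No size can be put on it, because the documents give neither the number of such men nor any donation rate. The practical effect depends on Section 5.1: either sites have conflicting instructions, or these men are released from the ban. PK similarity, sample size and power are unaffected.

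The conclusion rests on the ordinary reading of a plural, unlimited exemption and on applying the Section 10.3.1 definition to partners.

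**What to change.** In Section 10.3.2:

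1. Make the sperm-donation ban a separate bullet for all male participants, regardless of partner status, from Screening (signing the ICF) until at least 6 months after IP administration.
2. Limit the exemption explicitly to the condom/abstinence duty.
3. Have the sponsor confirm whether that duty was meant to cover partners of childbearing potential as well as pregnant or breastfeeding partners. If so, add them, and the exemption then has a clear role. If not, delete the exemption, since it would be nearly empty.
4. Align Section 5.1 (criteria 13 to 16) and the ICF.

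Steps 1 and 2 cost a few words. Step 3 needs a decision by the sponsor and, if the duty is widened, one more sentence. Matching edits to Section 5.1 and the ICF may follow. No participants or study procedures are added.

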10.4 Risk Mitigation Table

Target System	Effect	Risk Mitigation
Infections and infestations	Very common: Upper respiratory tract infection (nasopharyngitis, pharyngitis, laryngitis and rhinitis) Common: Bacterial infections (such as cellulitis), lower respiratory tract infection (such as pneumonia), viral infections (such as influenza and herpes), bronchitis, sinusitis, superficial fungal infections, abscess Uncommon: Sepsis including septic shock, pyelonephritis Rare: Tuberculosis, opportunistic infections (such as invasive fungal infections [histoplasmosis, coccidioidomycosis, pneumocytosis], bacterial, atypical mycobacterial infection and protozoal), hepatitis B reactivation, bacterial arthritis, infective bursitis	 Standard monitoring as with all early phase trials Participants must test negative for β-D Glucan, Hep B, Hep C and HIV Participants will be excluded if they have an active infection or a history of recurrent or chronic infections Participants will be excluded if they have a history of tuberculosis or evidence of active or latent TB infection Restrictions to vaccination with a live vaccine before and after IP administration Inclusion of CRP monitoring as part of the regular safety laboratory assessments (see Section 1.3 [SOA])
Neoplasms	Uncommon: Neoplasms (such as skin cancer, squamous cell carcinoma and melanocytic naevus) Rare: Lymphoma, leukemia, melanoma, Merkel cell carcinoma Not known: Hepatosplenic T-cell lymphoma*, Kaposi's sarcoma	Participants will be excluded if they have a history of clinically relevant malignancies
Hematological system	Common: Leukopenia (including neutropenia), anemia Uncommon: Thrombocytopenia, pancytopenia Rare: Aplastic anemia, agranulocytosis	 Standard monitoring as with all early phase trials Participants will be excluded from this trial if they have a hemoglobin or platelet level outside of the reference range at screening. Participants must not have donated blood within 8 weeks prior to IP administration Participants must not donate blood for at least 3 months after IP administration
Immune System	Common: Allergic reactions (bronchospasm, hypersensitivity, urticaria), autoantibody positive Rare: Serious systemic hypersensitivity reactions (including anaphylactic reaction), vasculitis (systemic), sarcoidosis	 Standard monitoring as with all early phase trials Participants will be excluded from this trial if they have a history of relevant drug/food allergies or known/suspected hypersensitivity to golimumab, AVT05 or any of its constituents Inpatient stay to monitor for acute immune reactions

Target System	Effect	Ris	sk Mitigation
		4)5)	Staggered sentinel cohort dosing strategy Anaphylactic reactions will be managed in accordance with local guidelines detailed in site-specific study operation manuals
Renal and Urological System	Rare: Bladder disorders, renal disorders	1) 2)	Standard monitoring as with all early phase trials Additional assessments may be completed if indicated
Hepatic System	Common: Alanine aminotransferase increased, aspartate aminotransferase increased Uncommon: Cholelithiasis, hepatic disorders	1) 2) 3) 4)	Standard monitoring as with all early phase trials Monitoring of liver function tests as part of the regular safety laboratory assessments (see Section 1.3 [SOA]) Participants will be excluded if they have previous exposure to hepatitis B, C or HIV Additional assessments could be added depending on clinical requirements, including a fibro scan of the liver
Cardiovascular system	Common: Hypertension Uncommon: Arrhythmia, ischemic coronary artery disorders, Thrombosis (such as deep venous and aortic), flushing Rare: Congestive heart failure (new onset or worsening), Raynaud's phenomenon	1) 2) 3) 4)	Standard monitoring as with all early phase trials Participants must be normotensive to be included in the study Participants must have ECG recordings without signs of clinically relevant pathology prior to IP administration Local sites can perform additional safety assessments (ie, Holter monitoring and telemetry as per adaptive features)
Respiratory System	Common: Asthma and related symptoms (such as wheezing and bronchial hyperactivity) Uncommon: Interstitial lung disease	1)	Standard monitoring as with all early phase trials
Nervous system (including psychiatry)	Common: Dizziness, headache, paresthesia, Depression, insomnia Uncommon: Balance disorders Rare: Demyelinating disorders (central and peripheral), dysgeusia	1) 2)	Standard monitoring as with all early phase trials Participants with a history of demyelinating conditions will be excluded (see Section 5.2)

Target System	Effect	Risk Mitigation
Gastrointestinal system	Common: Dyspepsia, gastrointestinal and abdominal pain, nausea, gastrointestinal inflammatory disorders (such as gastritis and colitis), stomatitis Uncommon: Constipation, gastroesophageal reflux disease	 Standard monitoring as with all early phase trials Any self-reported GI disturbance will be investigated further with appropriate investigation
Skin & Connective Tissue	Common: Pruritus, rash, alopecia, dermatitis Uncommon: Bullous skin reactions, psoriasis (new onset or worsening of preexisting psoriasis, palmar/plantar and pustular), urticaria Rare: Lichenoid reactions, skin exfoliation, vasculitis (cutaneous), Lupus-like syndrome Not known: Worsening of symptoms of dermatomyositis	Standard monitoring and regular AE checks as with all early phase trials
Reproductive system	Uncommon: Breast disorders, menstrual disorders	 Specific contraceptive requirements will be in place for participants Contraceptive guidance will be used in inclusion criteria WOCBP will need evidence of negative pregnancy tests prior to dosing
Endocrine disorders	Uncommon: Thyroid disorder (such as hypothyroidism, hyperthyroidism and goiter), Blood glucose increased, lipids increased	 Standard monitoring as with all early phase trials Participants with known diabetes will be excluded from the study
Ophthalmology	Uncommon: Visual disorders (such as blurred vision and decreased visual acuity), conjunctivitis, eye allergy (such as pruritis and irritation)	 Standard monitoring as with all early phase trials Any self-reported visual disturbance will be investigated further with thorough examination
General disorders and administration site conditions	Common: Pyrexia, asthenia, injection site reaction (such as injection site erythema, urticaria, induration, pain, bruising, pruritus, irritation and paresthesia), chest discomfort Rare: Impaired healing	 Standard monitoring as with all early phase trials Regular injection site checks
Injury, poisoning and procedural complications	Common: Bone fractures	Standard monitoring as with all early phase trials

^{*}Observed with other TNF-blocking agents.

